11.0 Specimen Collection and Banking (if applicable)

Urine specimens will be collected for laboratory testing, including drug tests, pregnancy tests, and ethyl glucuronide (alcohol use biomarker) tests. For visits conducted entirely remotely, the participant will collect and test urine specimens with CLIA waived qualitative ethyl glucuronide (EtG) tests, UDS, and pregnancy tests for participants assigned female at birth, with results verified using video or photo capture. Blood will be collected for laboratory testing, including carbohydrate deficient transferrin and phosphatidylethanol (alcohol use biomarker) tests. No samples will be banked after the aforementioned assays are completed. All laboratory testing will occur at the Clinical Neurobiology Laboratory in the Institute of Psychiatry on the MUSC campus. For visits conducted entirely remotely, blood will not be collected for laboratory testing.

12.0 Data Management

Statistical Methods

Power and Sample Size

This Phase II proof-of-concept trial is powered on the primary hypothesis that there will be a clinically significant differential in the decrease in total standard alcohol drinks and drinks per drinking day during the final four weeks of treatment (weeks 5-8) in the NAC group compared to the placebo group. In the proposed study, the two treatment arms, NAC and placebo, will be assessed for differences in drinking behavior using general linear models. In a prior pilot trial assessing adolescent drinking behavior (N=11), our team noted an average total of 49 (SD=26) drinks with 5.5 (2.0) drinks per drinking day during the 4 weeks prior to study enrollment. Additionally, although the participants noted in our prior CUD trial were not required to exhibit AUD nor was treatment targeted at drinking behavior, the heavier drinkers in the study (upper quartile of total drinks prior to baseline, ≥ 24 drinks/30 days) reported a mean of 58 (SD=30; median=54 drinks) drinks during the 4 weeks prior to study entry.²⁶ In this sample of heavier drinkers, those randomized to placebo had a median 10.7% decrease in total drinks at the end of CUD treatment (last 4 weeks of study treatment) as compared to a median 33.0% decrease in total drinks in the NAC treated group. Assuming a more robust treatment effect when alcohol use is the therapeutic target, a 50% decrease in total drinks during the final 4 weeks of study treatment in the active treatment group, as compared to baseline, would be a clinically relevant treatment effect. We conservatively estimate a similarly more robust 20% decrease in total drinks in the placebo treated group. Assuming similar baseline drinking behavior to the adolescent study (baseline mean=49 drinks/4 weeks) and a similar group level variance estimate as in the baseline study data (SD=25), we will have 80% power with a 5% type I error rate to detect the clinically relevant difference between a 50% decrease in the NAC treated group and 20% decrease in the placebo treated group (equivalent to 25 total drinks versus 40 total drinks during the final 4 weeks of treatment) with 45 participants randomized to each treatment group (n=90 total). Additionally, we anticipate that retention may be a challenge in this population, and we anticipate a 25% drop-out rate during study treatment, inflating the necessary randomized sample size to n=60 participants per treatment arm (N=120total randomized participants). The noted sample will have greater than 90% power to find a

Version: 16; Version Date: 11JULY2023

corresponding 50% decrease in drinks per drinking day in the NAC treated group as compared to a 20% decrease in the placebo treated group [2.8 (SD=2.0) vs. 4.4 (2.0) drinks per drinking day].

Primary Data Analysis

Baseline clinical and demographic characteristics will be collected and contrasts of baseline characteristics and clinical predictors of substance use will be performed between groups. Continuous and ordinal characteristics will be compared using a Wilcoxon Rank-Sum test statistic while categorical characteristics will be compared using a Pearson Chi-Square test statistic. If a baseline characteristic is significantly associated with the outcomes of interest, the corresponding variables will be used as initial covariates in the model analyses. Secondarily, possible covariates will be tested for confounding effects on the models specified and when present, they will be included in the final adjusted model. Specific Aim 1: The primary measure of interest will be the estimated reduction in self-reported standard alcohol drinks and the associated variance around these estimates during the final four weeks of study treatment (weeks 5-8) in those randomized to NAC as compared to those randomized to placebo. The main effect of NAC versus placebo on the total number of standard drinks will be assessed using generalized linear models and modelbased means with associated standard errors will be reported. Analytic models will be computed both unadjusted and adjusted for significant covariates and confounders found in the preliminary analysis. Specific Aim 2: Self-reported drinking (weekly TLFB and mobile technology-delivered daily diary) as well as biomarkers of recent alcohol use (EtG, CDT, PEth, and alcohol breathalyzer) will be collected at study visits. Agreement between collection measures will be measured as percent agreement and kappa coefficients. Agreement will be assessed weekly during the entire time course of the treatment study and deviations between self-reported moderate/heavy use and biomarker-indicated moderate/heavy use will be assessed to characterize the reporting (under-reporting) of self-reported use amounts. Similarly, medication adherence will be measured at weekly study visits using self-report (self-report and mobile technology delivered video) and MEMS. Concordance percentages and kappa coefficients will be calculated between the adherence measurement methods. Due to high prevalence of self-reported adherence in substance use disorder studies, kappa coefficients will be calculated as the prevalence adjusted bias adjusted kappa (PABAK).⁶² Clustered logistic regression model using the methods of generalized estimating equations will be applied to assess the differences in self-reported drinking and medication adherence measurement methods on binary adherence outcomes over time.⁶³ Working correlation structures will be independently compared and the final model structures will be chosen using the quasilikelihood under the independence model criterion statistic.⁶⁴ The main effects of measurement method and visit, as well as the interaction between method and visit, will examined for significance.

All randomized participants will be included in the primary analysis (intent-to-treat; ITT) and all statistical models will be implemented using SAS v. 9.4.

Secondary Data Analysis

In addition to the primary use outcome, secondary models will assess overall alcohol abstinence, the proportion of drinking days and the proportion of heavy drinking days noted during the final 4 weeks of study treatment. The temporal pattern in weekly drinking behavior over the course of the entire study is also of interest. Weekly drinking data in this population is likely to follow a Poisson distribution and will be assessed using random effects Poisson/Negative Binomial models and in the case of a high number of participants achieving abstinence from weekly alcohol use, zero inflated models will be explored. Similarly, binary weekly abstinence data will be assessed using mixed effects logistic regression models to assess the log-odds of weekly abstinence in the NAC- versus-placebo treated participants. Durability of treatment effects will be assessed through analysis of post-treatment alcohol use data at the Week 12 and Week 26 post-treatment visits, using model development processes similar to Specific Aim 1.

To assess the association between alcohol use reduction and changes in functional outcomes (alcoholrelated problems; alcohol craving; cognitive task performance; anxiety, mood, and sleep quality measures; quality of life), general linear regression models will be developed. Outcome specific distributions will be used to model functional and cognitive outcomes (e.g., count, binary and Gaussian). For Gaussian distribution assumptions, residual normality will be assessed using QQ plots, and when deviations from normality occur appropriate transformations will be made.

Missing Data and Attrition

Missing data are common in longitudinal alcohol clinical trials where use rates are the primary end point. The primary cause attributed to such missing data is participant attrition. Attrition can introduce bias into the parameter estimate and reduce study power, estimate precision and generalizability. In order to minimize missing data and study attrition, study simplification and enhanced communication between study coordinators and participants will be emphasized. We will make every effort to prevent attrition, e.g., phone/text/email reminders prior to visits, compensation for participation, meeting with participants in community if needed, and reinforcing adherence at each visit. However, these methods do not ensure that all data will be collected and appropriate analysis methods will be employed to accommodate missing data. Simply replacing missing data with the last observation carried forward or using worst case scenario adds substantial bias to both parameter and variance estimates.65,66 Maximum likelihood methods (ML) yield valid inferences assuming ignorable attrition (i.e., attrition is accounted for by covariates or the dependent variable measured prior to dropout). Additionally, Full Information Maximum Likelihood methods (FIML) will be implemented and compared to the results from the ML estimation to assess bias that may be present due to missing data.⁶⁷ In addition, in keeping with the Intent to Treat Principle, we will make every effort to continue assessments for the entire course of randomized treatment, even among those who fail to adhere to randomized assignment or stop participating in the study assigned intervention.

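### The 80% power for total drinks rests on SD 25 and a 15-drink difference; the pilot figures the plan cites (49, SD 26) give 14.7 drinks and about 76% at 45 per arm

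*Combined protocol and SAP*

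**What the plan says.** All the inputs stand in the combined protocol and SAP, Section 12.0, under Power and Sample Size.

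- **Source data.** The pilot is introduced with "In a prior pilot trial assessing adolescent drinking behavior (N=11"), and its result follows: "our team noted an average total of 49 (SD=26) drinks with 5.5 (2.0) drinks per drinking day" in the four weeks before enrolment. A second sample, the heavier drinkers in the earlier cannabis trial, "reported a mean of 58 (SD=30; median=54 drinks) drinks during the 4 weeks prior to study entry".
- **Inputs entered.** The mean is carried over from the pilot: "Assuming similar baseline drinking behavior to the adolescent study (baseline mean=49 drinks/4 weeks"). The variance is described as "a similar group level variance estimate as in the baseline study data (SD=25").
- **Effect.** A 50% decrease on NAC and a 20% decrease on placebo are said to be "equivalent to 25 total drinks versus 40 total drinks during the final 4 weeks of treatment".
- **Claim.** Power is 80% at a 5% type I error rate "with 45 participants randomized to each treatment group (n=90 total"). This is raised to 60 per arm for 25% drop-out.
- **Companion calculation.** Power above 90% is claimed for "2.8 (SD=2.0) vs. 4.4 (2.0) drinks per drinking day".

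**The concern.** The paragraph carries the pilot mean of 49 into the calculation unchanged but not the pilot SD. The two SDs reported for total drinks are 26 and 30. Neither is 25, and no other source is given. For drinks per drinking day the pilot SD of 2.0 is used as reported, so total drinks is the only outcome whose SD departs from the pilot.

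The drink counts also do not match the stated percentages. Measured against 49, totals of 25 and 40 are decreases of 49.0% and 18.4%, not 50% and 20%.

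Both departures push power upward, and the calculation has no slack: 45 is the smallest number per arm that reaches 80% with the inputs entered. The 80% is the stated design property for the primary outcome. A reader cannot recover it from the data the plan cites.

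**Working it through.** **Method.** Two-sample t-test with equal arms and two-sided α = 0.05; power from the noncentral t distribution with 2n − 2 degrees of freedom and noncentrality δ / (SD × √(2/n)). The plan does not state sidedness. Its inputs give 80.4% two-sided and 88.1% one-sided, so only the two-sided test matches its 80%.

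**1. The plan's own figure.** δ = 40 − 25 = 15, SD = 25, n = 45.
- Noncentrality = 15 / (25 × √(2/45)) = 2.85, and power = 80.4%. With 44 per arm it is 79.5%, so 45 is the minimum.
- Drop-out: 45 / (1 − 0.25) = 60.

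Both figures reproduce. The formula and the inflation are correct.

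**2. The effect in drinks.**
- NAC: 49 × 0.50 = 24.5
- Placebo: 49 × 0.80 = 39.2
- Difference: 39.2 − 24.5 = 14.7
- In reverse: 1 − 25/49 = 49.0%, and 1 − 40/49 = 18.4%

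**3. Power at 45 per arm.**

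| Difference | SD | What changes | Power |
|---|---|---|---|
| 15 | 25 | nothing (as entered) | 80.4% |
| 14.7 | 25 | drink counts only | 78.8% |
| 15 | 26 | SD only | 77.2% |
| 14.7 | 26 | both (pilot values) | 75.6% |

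Either correction alone takes power below 80%. The SD accounts for about 3 points and the drink counts for about 1.6.

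**4. Number needed for 80% at 14.7 and SD 26.** Power is 79.9% with 50 per arm and 80.7% with 51, so 51 evaluable are needed. From 60 randomized per arm, that allows 1 − 51/60 = 15% drop-out, against the 25% planned.

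**5. Precision of the pilot SD.** For SD 26 from 11 people, assuming normality, the 95% interval uses chi-square with 10 degrees of freedom (quantiles 3.247 and 20.483):
- Lower: 26 × √(10/20.483) = 18.2
- Upper: 26 × √(10/3.247) = 45.6

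With 14.7 drinks and 45 per arm, power is about 97% at the lower limit and 33% at the upper.

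**6. Companion outcome.** 5.5 × 0.50 = 2.75 and 5.5 × 0.80 = 4.4. The plan rounds 2.75 to 2.8, so its difference is 1.6. With SD 2.0 and 45 per arm, power is 96%, and the claim of more than 90% holds.

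**The case against.** The best defence is that nothing was miscalculated. SD 25 is an openly stated planning value, described only as similar to the baseline data, and 25 is similar to 26. The pilot SD is itself compatible with anything from 18 to 46, so one unit is well inside the noise. Nor is 26 better supported than 25 for the quantity tested: both are baseline figures, and the test uses totals from weeks 5-8. The drink-count rounding alone leaves 78.8%, close to 80%. Rounding in the companion calculation goes the other way, shrinking the difference from 1.65 to 1.6.

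In addition, 45 per arm is the number left after the planned loss. The plan includes all randomized participants, uses likelihood methods for missing data and foresees covariate-adjusted models. At 14.7 and SD 26, 60 per arm would give 86.7%.

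Much of this stands. The effect is small, the true power is uncertain in both directions, and the plan does disclose that the SD comes from 11 people before treatment. It does not settle the point, however. Calling the value similar does not give 25 a source. The 80% is claimed at 45 per arm, and 86.7% is a ceiling that needs weeks 5-8 data from everyone randomized. No correlation between baseline and outcome is given from which to size a gain from adjustment.

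**Conclusion.** The concern holds and is minor. The power formula and the inflation from 45 to 60 are correct; the inputs do not match the data cited for them. With the pilot's mean and SD and the stated percentage decreases, power at 45 evaluable per arm is 75.6%, or 78.8% if SD 25 can be sourced, against the stated 80%.

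These figures assume a two-sided 5% test, an unadjusted comparison of means, a common SD, and a weeks 5-8 SD equal to the baseline SD. The last assumption is the weakest. The plan gives no SD for the period tested and does not say how this limits the power statement, so true power could be higher or lower than any of these figures.

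**What to change.** In Section 12.0, Power and Sample Size:

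1. Use the reported SD of 26, or cite the data that give 25.
2. Replace 25 versus 40 drinks with 24.5 versus 39.2.
3. Restate the power, for example: *With 45 evaluable participants per arm (two-sided 5%, unadjusted), power to detect 24.5 versus 39.2 drinks is about 76% at SD 26 (79% at SD 25). The SD is a baseline value from 11 people (95% interval about 18 to 46, assuming normality). No SD for weeks 5-8 is available, so true power may be higher or lower.*

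The cost is two or three sentences and a lower stated power. Sample size, design and analysis do not change. The statement on drinks per drinking day can stay.

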Clinical Assessments

The instruments to be used were selected because many are standardized, have good psychometric properties, are widely used, and have been used by our research team.

Timeline Follow-Back, inclusive of detailed quantification of alcohol use, measured in standard drinks, will be conducted at baseline to characterize self-reported alcohol and other substance use.⁵³ This approach will be enhanced during trial participation by the implementation of mobile technology-delivered daily alcohol and other substance use reports, using methods established by our research team (see Preliminary Studies).⁴⁰ At baseline assessment and during each daily survey, participants are shown visuals and provided the definition of a standard drink to aid in reporting. The survey expires at midnight so that participants cannot access an old survey. A traditional Timeline Follow-Back will be conducted during laboratory visits to fill in missing data. These alcohol use quantification strategies will be used in calculating primary efficacy outcome measures, including total standard drinks, compared between the 4 weeks prior to intake and the last 4 weeks of study treatment. The trial is powered to test this primary outcome (see *Statistical Methods*), and other alcohol use-related outcomes are exploratory at this Phase II stage of investigation.

The MINI International Neuropsychiatric Interview will be conducted at the initial assessment visit to evaluate for psychiatric and substance use disorders.^{54,55} Throughout the study, a variety of self-report and clinician-administered measures (summarized in the **Study Timetable**) will be collected. In general, these measures will be used to assess and track mental health, substance use-related problems, quality of life, and other functional outcomes over the course of study participation as exploratory aims. Adverse events will

be documented, rated for severity and relatedness, coded in Medical Dictionary for Regulatory Activities (MedDRA) terms, and managed/reported appropriately via established procedures (see Human Subjects section). To evaluate penetration of the blind, participants and the primary study personnel who interact with the participant will be asked at multiple time points whether they think the participant is receiving NAC or placebo.

Laboratory Tests

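### The primary outcome is one raw weeks 5–8 drink total, with no adjustment for days observed and no rule for a partly observed window

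*Combined protocol and SAP*

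**What the plan says.** Section 10.0 (Clinical Assessments) defines the powered outcome as "total standard drinks, compared between the 4 weeks prior to intake and the last 4 weeks of study treatment". Section 12.0 (Primary Data Analysis) places it in weeks 5–8 and says that "The main effect of NAC versus placebo on the total number of standard drinks will be assessed using generalized linear models". No distribution, link, offset, per-day rate or minimum number of observed days is given.

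On who is analysed: "All randomized participants will be included in the primary analysis". On expected loss (Power and Sample Size): "we anticipate a 25% drop-out rate during study treatment".

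On gaps in the record, the plan says several things:
- Clinical Assessments: daily phone surveys expire at midnight, and "A traditional Timeline Follow-Back will be conducted during laboratory visits to fill in missing data".
- Study Timetable: daily reports confirmed by Timeline Follow-Back (TLFB) are marked at every visit, including Week 12 and the combined Week 26/early-termination column. No look-back length is given.
- Retention Strategies (Section 10.0): the intent-to-treat analysis is described as assuming drinking at each missed visit.
- Missing Data and Attrition (Section 12.0): worst-case and last-value replacement are rejected as biased. Maximum likelihood under ignorable attrition is planned, with a full-information (FIML) comparison and continued assessment after treatment stops.
- Secondary Data Analysis: weekly drinks are modelled with random-effects Poisson or negative binomial models, as a secondary analysis only.

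**The concern.** A sum over 28 days has its intended meaning only if all 28 days are known. With a quarter of participants expected to leave during treatment, some windows will be observed in part, and the plan does not say what their total is. With one total per person, the model sees a value or a blank. It cannot tell a 14-day sum from a 28-day sum. So a partial window is either entered short, which understates drinking, or dropped, which discards recorded data and departs from including everyone randomised. Likelihood estimation on that single outcome cannot recover the observed days in either case.

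The window is also loosely defined. For someone who stops early, the last four weeks of treatment and weeks 5–8 may be different periods.

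At stake is the one outcome the trial is powered for, and the effect size meant to inform Phase III. With the rule unstated, the choice could be made after the data have been seen.

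**Working it through.** **The plan's own figure.** Inputs from Power and Sample Size: "equivalent to 25 total drinks versus 40 total drinks during the final 4 weeks of treatment", SD 25, 5% type I error, 80% power. A two-sided test is assumed, as sidedness is not stated.
- n per arm = 2 × (1.96 + 0.842)² × 25² / 15² = 43.6, so 44 by the normal approximation. The t-based value is 44.6, so 45. This agrees with the plan.
- 45 / (1 − 0.25) = 60 per arm. This also agrees, and it shows that the sample size treats dropouts as lost, not as low scorers.
- Unrounded means: 49 × 0.8 = 39.2 for placebo and 49 × 0.5 = 24.5 for NAC, a difference of 14.7.

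**One participant, if recorded drinks are summed.** Constant daily drinking is assumed.
- Placebo, leaving at the end of Week 6: 39.2 × 14/28 = 19.6. Apparent decrease = 1 − 19.6/49 = 60%, against a true 20% and the 50% target for NAC.
- With 21 or 7 observed days, the apparent decrease is 40% or 80%.
- As a rate the value is recovered: 19.6/14 × 28 = 39.2.

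**Arm means, if recorded drinks are summed.** Assumptions, none of them in the documents: dropout proportion d is uniform over the eight weeks; those leaving in weeks 1–4 have no value; those leaving in weeks 5–8 are observed for half the window on average.

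Arm mean = μ × [(1 − d) + 0.5 × d/2] / [(1 − d) + d/2]

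- d = 15%: factor 0.8875/0.925 = 0.959
- d = 25%: factor 0.8125/0.875 = 0.929
- d = 35%: factor 0.7375/0.825 = 0.894

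| Dropout, placebo / NAC | Placebo mean | NAC mean | Difference | Change from 14.7 |
|---|---|---|---|---|
| 25% / 25% | 36.4 | 22.75 | 13.65 | −7% |
| 35% / 15% | 35.0 | 23.5 | 11.5 | −22% |
| 15% / 35% | 37.6 | 21.9 | 15.7 | +7% |

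**Upper end: all dropout inside weeks 5–8, half the window observed, 60 per arm, SD held at 25.**
- 25% in both arms: 14.7 × (1 − 0.25 × 0.5) = 12.9. Power falls from 0.90 to 0.81.
- No true effect (39.2 in both arms), 35% NAC and 15% placebo dropout: 39.2 × 0.925 − 39.2 × 0.825 = 3.9 drinks of false benefit. The standard error is 25 × √(2/60) = 4.56, and the rejection rate is about 14% instead of 5%.

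**The case against.** The strongest reply is that the plan contains no such scoring rule. A reader might infer that anyone who withdraws in weeks 5–8 is scored as having greatly reduced drinking. The documents do not support that. No section counts unobserved days as zero, attrition is treated as missing data, the sample size treats dropouts as lost, and Retention Strategies leans the other way by assuming drinking at missed visits. Data capture is also better than a clinic-only schedule: diaries arrive by phone, visits can be remote, assessment continues after medication stops, and TLFB is already scheduled at early termination and Week 12.

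This stands, and it makes every bias figure above conditional on summing what was recorded. The size is modest when dropout is equal. With 60 × 0.875 = 52.5 per arm analysed, z = 13.65 / (25 × √(2/52.5)) = 2.80, so power is still about 80%.

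A reader might also infer that the ±3-day window at Week 8 biases the comparison. It is symmetric and the same in both arms, so it gives no reason for a between-arm difference.

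What the reply does not supply is a value for a partly observed window. Assuming drinking at a missed visit gives no drink count, and it conflicts with the rejection of worst-case replacement. The weekly models could use partial data, but they are secondary.

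**Conclusion.** The point holds as a gap in the primary analysis for which a better method is available. The powered outcome is an unscaled total, partial windows are foreseeable, and the stated model can only shorten or drop them. It is not shown that the plan rewards withdrawal.

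If totals were summed as recorded, under uniform dropout the planned 14.7-drink difference would be 13.65 with equal 25% dropout and about 11.5 to 15.7 with 35%/15% imbalances. Equal loss shrinks the difference, and unequal loss favours the arm that loses more. These figures rest on constant daily drinking and on assumed dropout timing and imbalance, since the plan gives only the overall 25%. If partial windows were dropped instead, these figures would not apply. The cost would then be lost information and a primary analysis that does not include everyone randomised.

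**What to change.** 1. **Primary Data Analysis (12.0).** Define the window as study days 29–56 from randomisation, whatever the visit date. Then choose one of two models:
   - model drinks in the window with a log link and log(observed days) as an offset; or
   - make the weekly count model already planned as secondary the primary model, with observed days per week as exposure and the treatment contrast taken over weeks 5–8. Likelihood estimation then uses drinking recorded before dropout, including that of people who leave before Week 5.

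   Either model can report model-based means per 28 days, so the planned contrast stays readable.
2. **Clinical Assessments (10.0).** State that TLFB at the Week 8, early-termination or Week 12 visit covers every unreported day in the window up to that visit. From Week 12 (day 84) this is recall of 84 − 56 = 28 to 84 − 29 = 55 days. Do not rely on Week 26 (day 182), where recall would be 126 to 153 days. The Background itself warns that longer recall underestimates drinking.
3. **Retention Strategies (10.0) and Missing Data and Attrition (12.0).** Reconcile the assumption of drinking at missed visits with the likelihood approach that rejects worst-case replacement.
4. **Sensitivity analysis.** The offset assumes similar daily drinking before and after withdrawal, and it gives nothing for people with no observed day in the window. Add an analysis that varies post-withdrawal drinking and covers those participants.

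The cost is protocol and SAP wording, modest extra programming, and somewhat longer recall for the few who return late. The sample size does not change. The rule should be fixed before unblinding.
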